## **7.2. Demographic and Other Baseline Characteristics**

Demographics and other baseline characteristics will be summarized for the Safety Set by actual treatment and overall and for the ITT Set, the mITT Set, the PPS, and the mPPS by randomized treatment group and overall. Summary statistics and by-subject listings will be provided. The summary will be repeated for all subjects who enter Stage 2.

Demographics and baseline characteristics will include age, sex, ethnicity, race, weight, height, body mass index (BMI), age strata (< 9; >= 9 years), and refractive error (less myopic: SER -0.50 to -3.00 D; more myopic: one or more eyes with SER -3.01 to -6.00 D).

Age at Study day 1 = ((Study day 1) visit date - date of birth + 1) / 365.25 and truncated to complete years.

Height (in cm) = height (in inches) \* 2.54

Weight (in kg) = weight (in lbs.) \* 0.4536

BMI (kg/m^2) = Weight(kg)/[Height(m)]

## **7.3. Baseline Disease Characteristics**

Baseline values for spherical equivalent refraction (SER), astigmatism, anisometropia, axial length, and crystalline lens thickness will be summarized using descriptive statistics for Safety Set by actual treatment, and for the ITT Set, the mITT Set, the PPS, and the mPPS by randomized treatment group and overall. Summary statistics and by-subject listings will be provided. The summary will be repeated for all subjects who enter Stage 2.

## **7.4. Medical History**

A summary table of the number and percentage of subjects of ocular and other medical history by system organ class (SOC) and preferred term (PT) will be produced from the Safety Set. Medical history will be sorted alphabetically by SOC and in descending order of subjects per preferred term within each SOC.

All Medical history will be coded using the Medical Dictionary for Regulatory Activities (MedDRA) version 20.1 or higher.

A separate by-subject listing of medical history will also be provided.

## **7.5. Medication**

All prior and concomitant medications will be summarized based on classification using the Anatomical Therapeutic Chemical (ATC) classification and preferred drug name from the World Health Organization Drug Dictionary, version Sep2017, or later. Concomitant medications will be summarized for each stage separately.

A separate by-subject listing of medications will also be provided.

This document is confidential.

#### 7.5.1. Prior Medication

Prior medications are defined as medications entered in the eCRF that either start, or end before the first dose of study medication. Prior medications will be summarized by ATC level 2 and preferred drug name for the Safety Population.

Prior medications which continue after first dose of study medication will also be classified as a concomitant medication

#### 7.5.2. Concomitant Medication

Concomitant medications are defined as medication on the eCRF that are taken on or after or are ongoing at the start date of dosing for each stage. Concomitant medications will be summarized by ATC level 2 and preferred drug name for the Safety Set for each stage.

This document is confidential.

## 8. Efficacy

The primary and all secondary endpoints comprise a fixed sequence set of endpoints to be tested in the order given below. All statistical testing will be performed using a two-sided testing procedure with  $\alpha=0.05$ . Summaries of change for Stage 2 will include change from baseline and change from Stage 2 baseline (Month 36).

The order for the fixed sequence of endpoints to be tested are:

1. Between-treatment group (Atropine Sulfate Ophthalmic Solution, 0.02% versus Vehicle) difference in the proportion of subjects' eyes who show less than 0.5 D myopia progression (SER) from baseline at the Month 36 visit. (Primary Endpoint)
2. Between-treatment group (Atropine Sulfate Ophthalmic Solution, 0.02% versus Vehicle) difference in the mean change from baseline in SER at the Month 36 visit.
3. Between-treatment group (Atropine Sulfate Ophthalmic Solution, 0.01% versus Vehicle) difference in the proportion of subjects' eyes who show less than 0.5 D myopia progression (SER) from baseline at the Month 36 visits.
4. Between-treatment group (Atropine Sulfate Ophthalmic Solution, 0.01% versus Vehicle) difference in the mean change from baseline in SER at the Month 36 visit.
5. Between-treatment group (Atropine Sulfate Ophthalmic Solution 0.02% versus Vehicle) difference in the mean change from baseline in axial length at the Month 36) visit,
6. Between-treatment group (Atropine Sulfate Ophthalmic Solution 0.01% versus Vehicle) difference in the mean change from baseline in axial length at the Month 36 visit.

Not all sites used the same Vertex distance (VD) in mm when measuring refraction with autorefractor. All averaged SER measurements for each participant used in tables and analyses will be normalized to a VD of 0 mm to the corneal plane. The normalization (Fannin 1987) will be applied using

$$\text{Normalized SER} = \frac{100}{\frac{100}{\text{SER}} - \frac{\text{VD}}{10}}$$

where SER is the original SER from CRF.

The normalized SER will be used in all efficacy analyses for SER. SER values for randomization and stratification will not be normalized. Baseline SER will be normalized for use in the statistical analyses of efficacy. Both the original SER (from CRF) and normalized SER will be presented in listings. The astigmatism value for eligibility purpose will not be normalized because normalization to the corneal plane from a spectacle plane will always lead to a less minus power and hence will not change astigmatism eligibility for enrolled participants

This document is confidential.

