# Inclusion of the Modified Amblyopia Treatment Index (ATI), quality of life (QoL) questionnaire

At Month 42 and Month 48, in addition to other assessments, the study staff will encourage participation in the Modified Amblyopia Treatment Index (ATI), quality of life (QoL) questionnaire which has been added to the study to be completed by the subject and their parent/guardian. Participation is voluntary and will be documented. The parent/guardian questionnaire should be completed prior to the subject's questionnaire. The questionnaires should be completed prior to the Investigator's examination of the subject.

All subjects are to be re-consented/re-assented at their next study visit, including subjects completing an End of Study (EOS) Visit (Stage 1 – Month 36, Month 39, Month 42, Month 45, and Month 48).

**Number of Subjects (Planned):** Subjects will be randomized in a 2:2:3 ratio of vehicle: Atropine Sulfate Ophthalmic Solution, 0.01%: Atropine Sulfate Ophthalmic Solution, 0.02%

The target number of subjects to be randomized into the 6- to 10-year age group (436), the primary efficacy population, will be:

- Vehicle (placebo): 125
- Atropine Sulfate Ophthalmic Solution, 0.01%: 125
- Atropine Sulfate Ophthalmic Solution, 0.02%: 186

Approximately 483 subjects over all eligible ages will be enrolled, resulting in the following numbers of subjects in each arm:

- Vehicle (placebo): 138
- Atropine Sulfate Ophthalmic Solution, 0.01%: 138
- Atropine Sulfate Ophthalmic Solution, 0.02%: 207

The Sponsor may conduct a sample size re-estimation based on a masked assessment of the primary endpoint response rate and/or the subject discontinuation rate.

The randomization will be stratified twice: (1) by age at randomization (subjects  $\leq$  9 years; subjects  $\geq$  9 years) and (2) by refractive error (less myopic: SER -0.50 to -3.00 D; more myopic: one or more eyes with SER-3.01 to -6.00 D). The stratification is used to balance these characteristics across the 3 treatment groups. Enrollment will proceed until 436 subjects aged 6 to 10 years have been randomized and at least 483 subjects overall have been randomized. Enrollment may be closed

to subjects age  $\geq$  11 years following enrollment of 50 subjects into this age group to avoid over-enrollment into the study.

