#### **Primary Efficacy Endpoint:**

The primary efficacy endpoint is the between-treatment group (Atropine Sulfate Ophthalmic Solution, 0.02% versus Vehicle) difference in the proportion of subjects who show < -0.50 D myopia progression (SER) at the Month 36 visit.

The primary and all secondary endpoints comprise a fixed sequence set of endpoints to be tested in order. A 2-sided significance level of 0.05 will be adopted.

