#### **3.5.1. Atropine Sulfate Ophthalmic Solution, 0.02%**

A Fisher's exact test with a 0.05 two-sided significance level will have 95% power to detect the difference between an Atropine Sulfate Ophthalmic Solution, 0.02% responder proportion of 0.25, and a Vehicle responder proportion of 0.07 when the sample sizes are 136 and 91, respectively.

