#### **3.5.2. Atropine Sulfate Ophthalmic Solution, 0.01%**

A Fisher's exact test with a 0.05 two-sided significance level will have 90% power to detect the difference between an Atropine Sulfate Ophthalmic Solution, 0.01% responder proportion of 0.25, and a Vehicle responder proportion of 0.07 when the sample size in each group is 91.

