This document is confidential.

Header	Table Number	Name	Analysis Set
	14.2.3.3.2	Analysis of the New Prescriptions Given After the Start of Treatment due to Progression, at Month 36 Cochran-Mantel-Haenszel Test	Stage 1 Intent-to-Treat Set
14.2.3.4		Subjects who Progressed to High Myopia (Normalized SER -6.00 D or more myopic) at Month 36	
	14.2.3.4.1	Analysis of the Proportion of Subjects who Progressed to High Myopia (Normalized SER -6.00 D or more myopic) at Month 36 by Baseline Myopia Mixed Effects Model	Stage 1 Modified Intent-to-Treat Set
	14.2.3.4.2	Analysis of the Proportion of Subjects who Progressed to High Myopia (Normalized SER -6.00 D or more myopic) at Month 36 by Baseline Myopia Mixed Effects Model	Stage 1 Intent-to-Treat Set
14.2.3.5		Interaction between Demographic Variables and Normalized SER	
	14.2.3.5.1.1	Analysis of the Change from Baseline in Normalized SER (D) in Stage 1 by Treatment Group and Visit (6-8 years old vs. 9-10 years old) Mixed Effect Model	Stage 1 Modified Intent-to-Treat Set
	14.2.3.5.1.2	Summary of the Change from Baseline in Normalized SER (D) in Stage 1 by Treatment Group and Visit (6-8 years old vs. 9-10 years old)	Stage 1 Intent-to-Treat Set
	14.2.3.5.2.1	Analysis of the Change from Baseline in Normalized SER (D) in Stage 1 by Treatment Group and Visit (Baseline SER -0.50 to -3.00 D versus -3.01 to -6.00 D D) Mixed Effect Model	Stage 1 Modified Intent-to-Treat Set
	14.2.3.5.2.2	Summary of the Change from Baseline in Normalized SER (D) in Stage 1 by Treatment Group and Visit (Baseline SER -0.50 to -3.00 D versus -3.01 to -6.00 D D)	Stage 1 Intent-to-Treat Set

This document is confidential.

Header	Table Number	Name	Analysis Set
	14.2.3.5.3.1	Analysis of the Change from Baseline in Normalized SER (D) in Stage 1 by Treatment Group and Visit (Asian vs. Non-Asian) Mixed Effect Model	Stage 1 Modified Intent-to-Treat Set
	14.2.3.5.3.2	Summary of the Change from Baseline in Normalized SER (D) in Stage 1 by Treatment Group and Visit (Asian vs. Non-Asian)	Stage 1 Intent-to-Treat Set
	14.2.3.5.4.1	Analysis of the Change from Baseline in Normalized SER (D) in Stage 1 by Treatment Group and Visit (Dark Irides vs. Light Irides) Mixed Effect Model	Stage 1 Modified Intent-to-Treat Set
	14.2.3.5.4.2	Summary of the Change from Baseline in Normalized SER (D) in Stage 1 by Treatment Group and Visit (Dark Irides vs. Light Irides)	Stage 1 Intent-to-Treat Set

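### SER is converted to the corneal plane while the 0.50 D, 0.75 D and -6.00 D cut-offs keep their numbers, which modestly shifts what a responder or high myopia means; separately, the printed formula fails at SER 0.00 D

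*SAP*

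**What the plan says.** SAP Section 8 explains that sites did not all use the same VD on the autorefractor. All averaged SER values used in tables and analyses therefore "will be normalized to a VD of 0 mm to the corneal plane", by 100/(100/SER - VD/10). The converted value serves every SER efficacy analysis, baseline included. The exception is that "SER values for randomization and stratification will not be normalized". The same section remarks that conversion always gives a less minus power, but uses this only to argue that astigmatism eligibility is unaffected. Section 12 lists the conversion as a change from the protocol and does not mention the cut-offs.

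The protocol defines the primary endpoint on subjects "who show < -0.50 D myopia progression (SER) at the Month 36 visit", with no conversion. Entry allows SER down to -6.00 D as measured by cycloplegic autorefraction. In SAP Section 16 the cut-offs keep their numbers and are applied to converted SER: 0.5 D and 0.75 D for the responder tables, -0.75 D for time to progression, and, for high myopia, "Subjects who Progressed to High Myopia (Normalized SER -6.00 D or more myopic) at Month 36".

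Section 8.1.1 analyses the primary endpoint as observed, with no imputation.

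**The concern.** Bringing all sites to one plane is sensible. At 0 mm, however, a minus refraction and a change in it are both numerically smaller than at the plane where they were measured. Leaving the cut-offs at the same number of dioptres therefore changes the rule. A measured progression of exactly 0.50 D is not a response under a strict less-than-0.50 D rule, but it can become one after conversion. The amount depends on baseline myopia and on the site's VD, so one fixed rule becomes a sliding one. In the same way, -6.00 D means one refraction at entry and another in the high-myopia endpoint.

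This touches the first and third tests in the fixed sequence (0.50 D responders for 0.02% and for 0.01%), the tertiary 0.75 D and time-to-progression endpoints, and high myopia.

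The second matter is one of coding. The formula as printed divides by SER. An eye at exactly 0.00 D has no converted value and would drop out of the as-observed analysis, although an eye that started at -0.50 D or worse and reads 0.00 D is plainly a responder.

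**Working it through.** **The plan's own figure.** SAP 3.5.1: "A Fisher's exact test with a 0.05 two-sided significance level will have 95% power to detect the difference between" a 0.02% "responder proportion of 0.25, and a Vehicle responder proportion of 0.07 when the sample sizes are 136 and 91, respectively". Exact enumeration of Fisher's test gives 95.6%, which agrees with the stated 95%. For the 0.01% arm, with a Vehicle "responder proportion of 0.07 when the sample size in each group is 91", it gives 90.1% against the stated 90%.

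**Inputs.** The formula and the 0 mm target come from SAP Section 8, the cut-offs from SAP Section 16, and the baseline range of -0.50 to -6.00 D from the inclusion criteria. VD is an assumption: 12 mm, with a range of 10-15 mm.

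**Direction.** With v = VD/1000, the printed formula equals N(s) = s/(1 - s·v). For two readings s1 and s2 at the same VD:

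N(s2) - N(s1) = (s2 - s1) / [(1 - s1·v)(1 - s2·v)].

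When s1 and s2 are negative and v > 0, both brackets exceed 1, so the converted change is always the smaller one. Example at 12 mm, from -3.00 to -3.50 D: 0.50/(1.036 × 1.042) = 0.463 D, which counts as a response.

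**Measured equivalents of the unchanged cut-offs.** The inverse is s = c/(1 + c·v). From -3.00 D at 12 mm, the converted baseline is -2.896 D. The limit is -3.396 D, which maps back to -3.540 D, a measured progression of 0.540 D. Results at 12 mm, with the 10-15 mm range in brackets:

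| Baseline (measured) | 0.50 D rule | 0.75 D rule | Measured 0.50 D converts to (12 mm) |
|---|---|---|---|
| -0.50 D | 0.509 (0.508-0.511) | 0.766 (0.763-0.770) | 0.491 |
| -3.00 D | 0.540 (0.533-0.550) | 0.813 (0.802-0.829) | 0.463 |
| -6.00 D | 0.578 (0.565-0.599) | 0.870 (0.849-0.902) | 0.433 |

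**High myopia.** A converted -6.00 D needs a measured -6.00/(1 - 0.072) = -6.47 D at 12 mm (-6.38 at 10 mm, -6.59 at 15 mm). An eye entering at a measured -6.00 D is analysed at -6.00/1.072 = -5.60 D.

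**Effect on rates and power (illustrative).** Assume normally distributed progression with SD 0.6 to 1.2 D, centred so that 7% and 25% fall below 0.50 D, and a measured-scale cut-off of 0.51 to 0.58 D. Neither the SD nor normality is in the documents.

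- Vehicle moves from 7% to 7.1-9.0%, and active from 25% to 25.3-29.4%.
- The odds ratio moves from (0.25/0.75)/(0.07/0.93) = 4.43 to 4.42-4.23.
- Exact power at 136 and 91 moves from 95.6% to 95.8-97.2%.

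**Zero.** At SER = 0.00 D the printed form contains 100/0. The form s/(1 - s·v) gives 0.00 D and matches the printed form at every other value.

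**The case against.** Much of the case on the other side stands.

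- *No plane is assigned to the cut-offs.* A reader might infer that 0.50 D and -6.00 D are spectacle-plane values. The protocol says only SER, and entry is simply as measured. What the documents do show is that the protocol set its cut-offs with no conversion.
- *The leniency is conditional.* It needs VD above 0 and the same VD at both visits. With 15 mm at baseline and 10 mm later, -3.00 to -3.49 D (measured 0.49 D) becomes 3.49/1.0349 - 3.00/1.045 = 3.372 - 2.871 = 0.501 D, so a response becomes a non-response.
- *Bias towards atropine might be inferred*, because the active responder rate rises by more percentage points. The rule is identical in all arms. In the illustration the odds ratio, the scale of the primary model, moves slightly towards 1, and power changes by less than 2 points.
- *A spectacle-plane reference might seem the only way to keep the protocol's dioptres.* With mixed VDs, no single reference does. At a reference of 12 mm, a measured -3.00 to -3.50 D taken at 13.5 mm becomes 3.50/1.00525 - 3.00/1.0045 = 0.495 D, again a response. The shift is smaller, but the corneal plane has the merit of not depending on the instrument setting.
- *The conversion is declared* in Section 12, and original SER is listed beside converted SER.
- *High myopia is tertiary*, outside the fixed sequence. On measured SER, an eye entering at exactly -6.00 D would already meet the rule at baseline.
- *SER 0.00 D should be rare.* It cannot occur at baseline and needs a hyperopic shift of at least 0.50 D. The eye is lost only if the formula is coded literally.

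The reply to the declaration point is that Section 12 declares the conversion and not its effect on the responder and high-myopia definitions. Parts of SAP 8.1.3 and 8.2 are not in the available text, so a sensitivity analysis on as-measured SER cannot be ruled out there. The table index lists none.

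**Conclusion.** The point holds in a limited form. The SAP changes the scale of SER and leaves the cut-offs at the same numbers, so the 0.50 D rule corresponds to about 0.51-0.58 D measured across the entry range at an assumed 12 mm (0.508-0.599 D over 10-15 mm). The high-myopia rule moves further, by about 0.47 D (0.38 to 0.59 D), away from the -6.00 D used at entry. These sizes rest on the assumed VD and on the same VD at both visits; at VD 0 nothing changes. The shift in rates also rests on an assumed distribution of progression.

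The consequence is for meaning and for absolute responder rates. The documents do not support reading it as bias between arms or as a threat to the primary conclusion, nor do they show that the corneal plane is the wrong choice. The failure at SER 0.00 D is a real but rare coding risk, and it is easily removed.

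**What to change.** 1. In SAP Sections 8 and 12, print the conversion as SER/(1 - SER × VD/1000). It is the Section 8 formula rearranged, and it returns 0 at SER 0.00 D.
2. State that the 0.50 D, 0.75 D and -6.00 D cut-offs are applied on the corneal plane, and list this in Section 12 as a change in the responder and high-myopia definitions.
3. Pre-specify a repeat of the 0.50 D, 0.75 D and high-myopia analyses on as-measured SER as a sensitivity analysis.

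Moving the primary analysis to a spectacle-plane reference is optional, since the choice of plane is debatable. The cost is one derivation line, some SAP wording and a few extra tables. No new data are needed, because original SER is on the CRF and already listed.

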## 8.1. Primary Efficacy Endpoint and Analysis

### 8.1.1. Primary Efficacy Endpoint

The primary efficacy endpoint is the between-treatment group (Atropine Sulfate Ophthalmic Solution, 0.02% versus Vehicle) difference in the proportion of subjects' eyes who show less than 0.5 D myopia progression (SER) from baseline at the Month 36 visit.

Spherical equivalent refraction will be measured using cycloplegic autorefractometry at Months 6, 12, 18, 24, 30, and 36. Subjects' eyes will be determined at each visit if they have a less than 0.5 D myopia progression (SER). All data collected through Month 36 will be used, regardless of when treatment is stopped. There will be no imputation for missing data; analysis will be conducted as observed.

The primary analysis will be performed using a Mixed Model based on the binomial distribution using a logit link function. Progression as the dependent variable, subject, treatment, visit, eye (left or right) and baseline age group (as randomized) and SER (as randomized) as independent variables and treatment by visit interaction term included. Random intercepts for subject and eye within subject will be included using variance components and compound symmetry covariance structures, respectively. The primary analysis will be performed using the mITT analysis set assuming data is missing at random.

```
proc glimmix data=master empirical method=quad;  
  class subjid trtpn(ref='0') avisitn eye agegr1 sergr1;  
  model eff(event='1') = trtpn avsitn eye agegr1 sergr1 trtpn*avisitn / dist=bin link=logit solution or;  
  nloptions tech=nrridg maxiter=25;  
  random intercept / subject=subjid type=vc;  
  random intercept / subject=eye(subjid) type=cs;  
  estimate '0.02% vs. Pbo Month 36' trtpn 0 1 -1 trtpn*avisitn 0 0 0 0 0 0 0 0 0 0 1 0 0 0 0 0 -1;
```

The absolute risk difference and associated Wald 95% CI will also be presented at Month 36 using the following frequency procedure.

```
proc freq data=dat order=data;  
  tables trtpn*eff / riskdiff(equal cl=wald);
```

Counts and percentage of subject' eyes progressing at each visit for each stage will be summarized. For the primary endpoint and associated secondary endpoints, Odds Ratios, 95% confidence interval (CI), and p-value will be provided along with an accompanying figure.

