### **3.5. Determination of Sample Size**

For the purposes of the study and identifying sample size, a responder is defined as a subject with a  $> -0.50$  D myopia progression (SER) from baseline at a given time point.

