#### 8.1.5. Other Analysis of the Primary Endpoint

The primary analysis will be repeated for the ITT and PPS analysis sets and for each stratification level. Sensitivity analyses will be repeated for the ITT population only. There will be no imputation for missing data; analysis will be conducted as observed. The analysis will be conducted using the same model as the primary efficacy analysis (as described in 8.1.1 above).

As part of the sensitivity analyses for the primary efficacy analysis, the point estimate and 95% Wald confidence interval, for the absolute difference in the proportions of subjects with less than 0.50D myopia progression (SER) at Month 36 between the treatment groups without any models should be presented.

This document is confidential.

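### The Month 36 risk difference in SAP 8.1.1 has an unclustered Wald interval and no stated unit; on eye records it is about 18% to 25% too narrow (assumed between-eye correlation 0.5 to 0.8)

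*SAP*

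**What the plan says.** SAP 8.1.1 sets the primary endpoint on eyes: "Subjects' eyes will be determined at each visit if they have a less than 0.5 D myopia progression (SER". The mixed logistic model for it carries "random intercept / subject=subjid type=vc" and a second random intercept for eye within subject.

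The same section then promises a second output: "The absolute risk difference and associated Wald 95% CI will also be presented at Month 36 using the following frequency procedure". The code is "tables trtpn*eff / riskdiff(equal cl=wald", run on a dataset called `dat`, whereas the model runs on `master`. It has no subject, eye or cluster term, and the record unit of `dat` is not defined in the text reviewed. The sentence straight after the code again counts eyes: "Counts and percentage of subject' eyes progressing at each visit for each stage will be summarized".

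SAP 8.1.5 asks for a model-free Wald interval as a sensitivity analysis, but "for the absolute difference in the proportions of subjects with less than 0.50D myopia progression (SER) at Month 36", with no rule for combining two eyes. The only subject-level rule in the text reviewed is the at-least-one-eye composite of 8.1.2.1. Neither 8.1.1 nor 8.1.5 refers to it.

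**The concern.** Both eyes of every child are treated and measured, so eye records come in pairs that share a child. The Wald variance in PROC FREQ assumes independent rows. Run on eye records, it takes the sample to be twice the number of children, and the interval is too short whenever the two eyes are positively correlated. SAP 6.1 itself expects strong correlation between eyes, though it says so for continuous variables.

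The endpoint is worded as a difference in proportions, but the model's listed outputs are odds ratios. In the text reviewed, the unmodelled intervals of 8.1.1 and 8.1.5 are the only Month 36 estimates on the endpoint's own scale, so readers will judge absolute benefit from them. The `equal` option also requests a Wald test of no difference, which has the same fault.

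If `dat` holds one row per child, the variance is right. The estimate is then no longer the per-eye endpoint of 8.1.1, and it depends on a responder rule that neither passage states.

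**Working it through.** **Inputs.** SAP 3.5.1 gives responder rates of 0.25 (0.02% arm) and 0.07 (Vehicle): "a Vehicle responder proportion of 0.07 when the sample sizes are 136 and 91, respectively". These rates are per child, since "a responder is defined as a subject with a" given degree of progression (SAP 3.5). There are two eyes per child. The between-eye correlation ρ of the binary response is not in the documents; 0.5 to 0.8 is assumed, equal in both arms.

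**The plan's own figures.** Exact enumeration of the two-sided Fisher test gives 95.6% power for 136 against 91 (stated 95%) and 90.1% for 91 per group (stated 90%). Both reproduce.

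**Unclustered interval, planning rates read as per-eye rates.**

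SE = √[(0.25×0.75/136 + 0.07×0.93/91)/2] = 0.0324. The half-width is 1.96 × 0.0324 = 6.34 points, so the interval around 18 points is 11.7 to 24.3.

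**Clustered interval.** With two eyes per child the variance is multiplied by 1 + ρ. The unclustered interval is therefore too narrow by 1 − 1/√(1+ρ), and its coverage is 2Φ(1.96/√(1+ρ)) − 1.

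| ρ | Clustered half-width (points) | Clustered interval (points) | Unclustered too narrow by | Unclustered coverage |
|---|---|---|---|---|
| 0.3 | 7.23 | 10.8 to 25.2 | 12.3% | 91.4% |
| 0.5 | 7.77 | 10.2 to 25.8 | 18.4% | 89.0% |
| 0.8 | 8.51 | 9.5 to 26.5 | 25.5% | 85.6% |
| 1.0 | 8.97 | 9.0 to 27.0 | 29.3% | 83.4% |

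Simulation of paired eyes (20,000 trials per setting) gave unclustered coverage of 89.0% and 85.3% at ρ 0.5 and 0.8, against 95.0% and 94.9% with clustering.

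**Is 0.5 to 0.8 reasonable?** Suppose the SER changes of the two eyes are bivariate normal with an assumed correlation of 0.7 to 0.95.

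- At 0.7 the binary correlations are 0.469 (25% arm) and 0.383 (7% arm). The interval is 16.7% too narrow, with coverage 89.8%.
- At 0.95 they are 0.786 and 0.741. The interval is 24.8% too narrow, with coverage 85.9%.

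**The `equal` test.** With no true difference, the formula gives a rejection rate of 11.0% (ρ 0.5) or 14.4% (ρ 0.8) instead of 5%. Simulation at 7% in both arms gave 11.3% and 15.3% unclustered, and 5.2% and 5.5% clustered.

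**Planning rates read as at-least-one-eye rates (the 8.1.2.1 rule).** Solve p + (1−ρ)p(1−p) = 0.25 and 0.07 for the per-eye rate p.

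- ρ 0.5: per-eye rates 17.7% and 4.7%; half-width 5.5 unclustered against 6.7 clustered; clustered interval 6.2 to 19.7.
- ρ 0.8: per-eye rates 21.6% and 5.9%; half-width 6.0 against 8.0; clustered interval 7.7 to 23.7.

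The interval excludes zero in every case above.

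**The case against.** The error exists only if `dat` holds eyes, and several places point to children. The dataset is not the one used for the eye-level model. SAP 8.1.5 says subjects, and so does the primary endpoint in the protocol synopsis. The SAP's general rules (6.1 and 13.2.5.2) give categorical percentages per subject unless noted otherwise. Parts of SAP 8.1.2 to 8.1.3 and 8.2.1 to 8.2.3 are not in the copy reviewed, so a definition there cannot be excluded. The documents give no binary correlation, and the bivariate-normal check at 0.7 falls slightly below the 18% figure. Nothing says the `equal` p-value will be reported, and it has no place in the fixed testing sequence. The interval is not the primary inference.

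Much of this stands as a limit on size and certainty. It does not remove the problem. The general subject defaults yield to specific wording, and 8.1.1 is specific: its endpoint, its responder status and the sentence after the code are all per eye, and PROC FREQ uses the same response variable, `eff`, as the eye-level model. In the table index, the primary output (14.2.1.1.1) is titled by eyes, the only subject-level Stage 1 table at 0.5 D is the composite (14.2.1.2.1), and no separate risk-difference table is listed. A programmer following 8.1.1 as written would most naturally feed in eyes. If children were meant, the responder rule is still missing from both passages.

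**Conclusion.** The concern holds and should be fixed; confidence is medium because the unit of `dat` is inferred. On the natural reading of 8.1.1, the Month 36 risk-difference interval ignores the pairing of eyes. It is then about 18% to 25% too narrow, with coverage of about 89% to 86%. This assumes two eyes per child and a common binary correlation of 0.5 to 0.8; the ceiling is 29% and 83% at a correlation of 1. If `dat` has one row per child, the width is correct and the fault is an unlabelled change of endpoint unit without a responder rule.

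The damage is confined to this interval and its `equal` test. The mixed-model odds ratio, its interval and p-value, and the decisions of the testing sequence do not change.

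**What to change.** State in 8.1.1 whether `dat` has one record per eye or per child, and make 8.1.5 agree.

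- **If eyes:** replace the Wald interval with one clustered by subject. A binomial GEE with identity link, treatment as the only term, independence working correlation and robust standard errors by `subjid` keeps the PROC FREQ point estimate and corrects its error. A survey procedure with subject as cluster does the same job. A subject-level bootstrap of the standardised difference from the primary model is a third option for 8.1.1, but it is model-based and so does not meet the model-free request in 8.1.5. Drop the `equal` test or cluster it. Do the same for 0.01% against Vehicle if a risk difference is reported there.
- **If children:** name the rule that combines two eyes, and label the estimate as subject-level, distinct from the per-eye endpoint.

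The cost is one sentence and, for eyes, a few lines of code. The reported interval becomes wider. No new data and no change to the primary test are needed.
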